Children’s Dermatology Life Quality Index: This PRO will be completed using an iPad. The 10-item questionnaire designed for use in parents of children (i.e., ages 4-17) to obtain information on children’s quality of life (14, 15). It is self-explanatory and can be simply handed to the patient who is asked to fill it in with the help of the child’s parent or guardian. Each question relates to a component of quality of life: Symptoms/Feelings (items 1-2); Leisure (items 4-6); School (item 7); Relationships (items 3-8); Sleep (item 9), and Treatment (item 10). Children answer each question using a 4-point scale: Not at all = 0, A Little = 1, Quite A Lot = 2, Very Much = 3. The scores from each item are summed to create a severity burden score (i.e., maximum score = 30). The scores represent degree of severity burden on quality of life: No effect = 0-1; Small effect = 2-6; Moderate effect = 7-12; Very large effect = 13-18; and Extremely large effect = 19-30. This measure will be completed electronically on an iPad and data will be submitted directly to the secure RedCap database at the University of Rochester Medical Center.

Children’s Sleep Habits Questionnaire (CSHQ): This PRO will be completed using an iPad. This is a validated and abbreviated form of the original CSHQ containing 22 items instead of 45 items (16, 17). This abbreviated CSHQ questionnaire consists of 4 subscales: Bedtime, Sleep Behavior, Waking During the Night, and Morning Wake Up. The patient/parent will answer each item choosing from: “Always” if something occurs every night; “Usually” if it occurs 5 or 6 times a week; “Sometimes” if it occurs 2 to 4 times a week; “Rarely” if it occurs once a week; and “Never” if it occurs less than once a week. Each question is scored on a 3-point scale as 1 = Usually and Always (5-7 times/week); 2 = Sometimes” (2-4 times/week); or 3 = Rarely and Never (0-1 time/week). The scores are combined from each subscale to generate a Total Sleep Disturbance Score, which can range from 22 to 66. A Total Sleep Disturbances score over 28 represent clinically significant sleep disturbance. This measure will be completed electronically on an iPad and data will be submitted directly to the secure RedCap database at the University of Rochester Medical Center.

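### The single CSHQ scoring key gives the most frequent behaviours the lowest score although a higher total means worse sleep, and no item is reverse-scored

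*Combined protocol and SAP*

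**What the plan says.** The CSHQ paragraph of section 5.3 (Outcome Measures and Study Forms) describes an "abbreviated form of the original CSHQ containing 22 items instead of 45 items", with "4 subscales: Bedtime, Sleep Behavior, Waking During the Night, and Morning Wake Up". Answers are frequencies: Always applies "if something occurs every night", and the options run down to Never.

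One key covers every item: "Each question is scored on a 3-point scale as 1 = Usually and Always (5-7 times/week", then 2 for Sometimes, "or 3 = Rarely and Never (0-1 time/week". The items are combined into a Total Sleep Disturbance Score from 22 to 66. Its direction is set by the cut-off: "A Total Sleep Disturbances score over 28 represent clinically significant sleep disturbance".

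Section 1.4 names the 12-week change in CSHQ as a secondary outcome. It hypothesises lower severity (a change of at least 5) on at least one of sleep, anxiety and depression, with a larger improvement on crisaborole and a correlation with EASI. Section 11.2 applies the primary-analysis methods to sleep.

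**The concern.** The key and the total point in opposite directions for any item that describes a sleep problem. A frequency key on which the commonest behaviour scores 1 suits a disturbance total only where the behaviour is desirable. A subscale on night waking is hard to read that way: nightly waking would take the best score and no waking the worst.

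This does not look like a deliberate convention. In the same section the CDLQI, FDLQI and CBI all give more points to greater or more frequent problems, in line with their totals. For PROMIS Itch, scoring is handed to external conversion tables. The CSHQ has no such deferral, so the printed key is the only scoring rule the plan contains.

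At stake are the CSHQ change, its comparison between arms and its correlation with EASI. Because section 1.4 accepts any one of three domains, the sleep result alone could satisfy the severity part of the secondary hypothesis. The CSHQ is also the only secondary outcome collected for every pair: under section 5.1 children under 5 complete no self-report measures, while all caregivers complete the CSHQ.

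**Working it through.** **Inputs, all from the CSHQ paragraph of section 5.3:** 22 items; scores 1 (Usually/Always), 2 (Sometimes), 3 (Rarely/Never); cut-off above 28.

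**1. The plan's own range.** 22 x 1 = 22 and 22 x 3 = 66. The stated 22 to 66 is reproduced. It would be the same with the key reversed, so the range says nothing about direction.

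**2. One night-waking item.** Assume that it asks how often the child wakes. Improvement from Always to Never:
- printed key: 3 - 1 = +2, read as worse;
- key in line with the total: 1 - 3 = -2, read as better;
- error: (+2) - (-2) = 4 points.

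Two such items give 2 x 4 = 8 points, more than the change of 5 used in section 1.4.

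**3. The whole total.** The item wording is not given, so let m of the 22 items describe desirable behaviour and vary m. Under the printed key:
- perfect sleeper: m x 1 + (22 - m) x 3 = 66 - 2m;
- worst sleeper: m x 3 + (22 - m) x 1 = 22 + 2m.

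| m | Perfect sleeper | Worst sleeper | Perfect sleeper above 28? |
|---|---|---|---|
| 0 | 66 | 22 | yes |
| 6 | 54 | 34 | yes |
| 11 | 44 | 44 | yes |
| 18 | 30 | 58 | yes |
| 19 | 28 | 60 | no |
| 22 | 22 | 66 | no |

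A perfect sleeper is classed as not disturbed only if 66 - 2m <= 28, that is m >= 19.

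Going from worst to perfect sleep changes the total by (66 - 2m) - (22 + 2m) = 44 - 4m, where a correct key gives -44. That is +44 at m = 0, +20 at m = 6, 0 at m = 11 and -32 at m = 19. Below 11 the scale runs backwards overall; between 11 and 22 it runs the right way but is compressed.

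**4. What a total of 28 or less requires.** With a items scored 2 and b items scored 3, the total is 22 + a + 2b. It is at most 28 when a + 2b <= 6. Then a + b <= 6, so at least 22 - 6 = 16 items must be Usually/Always. If all the others are Rarely/Never, b <= 3 and at least 19 are needed.

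**5. With problem items reversed.** If problem items score Usually/Always = 3 and Rarely/Never = 1, and desirable items keep the printed key, a perfect sleeper scores 22 and the worst sleeper 66 for every m.

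**The case against.** The strongest reply is that the documents show four subscale titles and no item text. Whether a frequent answer is good or bad depends on the wording of each item, so the night-waking result is an inference and the net error cannot be fixed. This stands, which is why the figures above are given over a range of m. It does not remove the inconsistency: the printed key classes a perfect sleeper correctly only if at least 19 of the 22 items describe good sleep.

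A second reply is that the paragraph is only a short description of a validated instrument, and that the total may in practice be computed with the instrument's own key. That is possible. The documents say that answers go to REDCap but not where or how the CSHQ total is calculated; the remark on automatic scoring in section 5.3 concerns the PROMIS measures. This is a reason to check, not evidence that the scoring is right.

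A reader might infer more than the documents support:
- That the sleep comparison will come out with the wrong sign. The sign depends on the unknown mix of items and on the text being followed literally.
- That the 28 cut-off would distort a planned analysis. Section 11.2 plans none that classifies children by it, so misclassification would matter only for descriptive use.
- That all 22 items should simply be flipped. Items describing good sleep are already scored in the right direction.

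**Conclusion.** Section 5.3 contradicts itself on CSHQ scoring: one key for every item, a total on which higher is worse, a night-waking subscale and no reverse scoring. The error is 4 points for each problem item that moves between Always and Never. Across the total, the effect ranges from full reversal (m = 0) through complete cancellation (m = 11) to none (m = 22).

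The night-waking conclusion assumes that those items ask how often waking occurs, as the subscale title and the response wording suggest. The consequence for the results assumes that the printed key is the one applied. On those terms, the 12-week CSHQ change, its between-arm comparison and its correlation with EASI can be diluted or reversed. The primary outcomes and the sample size are not affected.

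**What to change.** Replace the single key in section 5.3 with an item-by-item key taken from the instrument's own scoring. Items describing a problem score Usually/Always = 3, Sometimes = 2, Rarely/Never = 1; items describing desirable behaviour keep the current key.

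Before analysis, confirm that this key is used wherever the total is computed, in REDCap or in an analysis script. A test that detects direction is to enter two artificial records: a pattern of good sleep on every item must score 22, and a pattern of bad sleep on every item must score 66. Checking only that totals lie between 22 and 66 would not find the fault.

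The cost is protocol wording and a scoring script, with no new data, provided item-level answers are stored. Settling the direction in advance also avoids a choice made after seeing the data in an open-label trial.

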#### **5.4. Randomization**

Randomization will assign a pediatric subject to one of two topical treatments (crisaborole or tacrolimus 0.03%) at a ratio of 1:1. Randomization will use a computerized pseudorandom number generator and will employ a random block size of 4 or 6. Study personnel will obtain randomization assignment in REDCap.

#### **5.5. Blinding Methods**

This is an open-label study and is not blinded.

#### **5.6. Subject Compliance**

Subject compliance will be assessed using tube weight of the assigned topical treatment. A tube of crisaborole and a tube of tacrolimus 0.03% will be weighed at the start of the study by study personnel to serve as the baseline weight for all subjects in the study. Study personnel will weigh the tube at 6 Weeks and 12 Weeks to ensure that the subject is using the topical treatment for atopic dermatitis.

## **5.7. Costs to Subject**

There is no cost to subjects for participation in this study. All study medications and study materials will be provided to the subject without cost.

## **5.8. Reimbursement for Participation**

All pediatric subjects will receive a \$10 gift card at the end of each study visit for their participation in this study (i.e., total \$30 in gift cards). All adult caregiver subjects will be reimbursed \$100 for completion of all study procedures. Payment will be prorated based on number of assessments completed in the study. Subjects will be paid \$20 for completion of Baseline Assessment, \$40 for completion of 6 Week Assessment, and \$40 for completion of 12 Week Assessment. A check will be issued to the adult caregiver (i.e., caregiver) after completion of 12 Week Assessment or whenever their participation in the study has ended.

## **6. CONCOMITANT AND DISALLOWED MEDICATIONS**

Systemic anti-inflammatory therapies for atopic dermatitis are allowed if the subject is taking a stable dose of the systemic anti-inflammatory medication for at least six week prior to enrollment. It must be anticipated that this stable dose would not change during their participation in this study, unless deemed medically necessary. Any changes in systemic medication dose due to flaring of atopic dermatitis or side effects will be documented on the *AD Flare Medication Form* and *AE Source Doc* (see page 19). These therapies are not usually used in children with atopic dermatitis of moderate or less severity. If a subject is newly prescribed systemic anti-inflammatory therapy during the course of the study due to worsening atopic dermatitis, the subject will be withdrawn from the study.

## **7. SUBJECT WITHDRAWALS**

Subjects will be advised during the consent/assent process that they have the right to withdraw from the study at any time without prejudice or reason. Criteria for investigator-initiated subject withdrawal include: inability to make study visits, subject lost to follow-up, non-compliance to study procedures, or death. The reason for discontinuation will be recorded in the subject's medical records. The date of occurrence and reasons for any subject withdrawal will be recorded and documented on the **Withdrawal Form**. Subjects that withdraw from the study will be replaced with another subject.

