- Study personnel will add appropriate subject information and study progress to the **Comprehensive Study Log**, as required by RSRB. This log is a password-protected excel file located in the study folder on the Dermatology CTU’s University sharedrive. Study personnel will only have access to this study folder and excel file.
- Subjects will be on study for at least 12 weeks. Subjects will be assessed at three different time points (Baseline, 6 Weeks, and 12 Weeks). Each assessment will be performed in the dermatology clinic and take approximately 30 minutes or less
- Pediatric subjects will be randomized 1:1 to one of two topical treatments: crisaborole or tacrolimus 0.03%. Both of these topical treatments are standard care for mild to moderate atopic dermatitis. Study personnel will obtain randomization in REDCap. After randomization, the treating dermatologist (i.e., [REDACTED]) will prescribe crisaborole or tacrolimus 0.03% to the pediatric subject for treatment of atopic dermatitis. Study personnel will dispense a tube of tacrolimus 0.03% or crisaborole to the subject based on randomization. The topical treatments will be applied to all affected areas twice daily for at least 12 weeks on this study. Additional tubes of tacrolimus 0.03% or crisaborole will be dispensed to the subject if needed to complete the 12 week treatment and assessment period. At the completion of the study, the treating dermatologist may continue or change the prescribed treatment for atopic dermatitis.
- Study personnel will complete the **ASPIRE On-Study Form** in REDCap. This form collects demographic information on both the pediatric subject and caregiver subject. Additionally, the form collects treatment information related to atopic dermatitis, all current medications, and medical history for the pediatric subject. This form will be completed after assent and consent are obtained.

- **Baseline Assessment:**
  - *Study personnel:* Trained study personnel (MD/NP) will perform Eczema Area & Severity Index (EASI), Investigator Static Global Assessment (ISGA), and Percentage Body Surface Area (%BSA) for the severity of atopic dermatitis. Study personnel will also weigh the tube of crisaborole and tacrolimus 0.03% prior to distribution to the subject. Study personnel will have an average weight for tube of tacrolimus prescribed. Study personnel will enter EASI, ISGA, and tube weight into the electronic **Assessment Form (Baseline)** in REDCap.

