  - *Pediatric Subjects:* Pediatric subjects ( $\geq 5$  years) will complete five self-report outcome measures (**PROMIS® Itch, PROMIS® Pain Interference, Children's Dermatology Life Quality Index (CDLQI), PROMIS® Anxiety, PROMIS® Depression**) on an iPad. All self-report measures can be completed with the assistance of their parent or guardian. All five self-report outcome measures can be completed in 20 minutes or less. Pediatric subjects  $< 5$  years will not complete any self-report measures on the iPad.
  - *Caregiver Subjects:* All caregivers will complete one self-report questionnaire about their child's sleep habits (**Children's Sleep Habits Questionnaire (CSHQ)**) and two self-report measures for caregiver burden (**Caregiver Burden Inventory (CBI)**) and quality of life (**Family Dermatology Life Quality Index (FDLQI)**) on an iPad. All self-report measures can be completed in 5 minutes.
- Pediatric subjects will complete a Pediatric Subject Reimbursement Form at the end of the Baseline Assessment. The pediatric subject will print their name, address, sign and date the form. The adult caregiver may help the child complete the form if he/she has difficulty writing. Pediatric subject  $\geq 5$  years must sign the form. Study personnel will give the pediatric subject a \$10 gift card after for the completion of this form for completion of the Baseline Assessment. For pediatric subjects  $< 5$  years, the adult caregiver will complete and sign the form. Study personnel will give the adult caregiver subject a \$10 gift card after for the completion of this form for completion of the Baseline Assessment.
- Study personnel will call the caregiver by phone during the Week 3 of treatment for adverse event monitoring of their child who is participating and on topical treatment. Study personnel will ask: 1) Has your child been able to use the topical treatment without any problems?; 2) Has your child experienced any burning from the topical treatment?; and 3) Has your child experienced any side effects or adverse reactions while using the topical treatment?. Study personnel will document the phone call in the Call Log. Adverse events will be documented on AE source doc.
- Study personnel will call the caregiver by phone at least 48 hours prior to the 6 Week Assessment to remind he/she of their upcoming appointment and to bring their tube of topical treatment with them to the appointment. Study personnel will also monitor for

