## **10. RISK/BENEFIT ASSESSMENT**

### **10.1. Potential Risks**

The proposed study is a low risk clinical trial. Subjects (patients & caregivers) will be completing self-report questionnaires at three different regularly scheduled clinic visits. The two topical treatments in the study are FDA-approved and standard care for  $\leq$ moderate atopic dermatitis. Crisaborole is approved for use in ages 2 years and older. Known side effects to crisaborole include pain at the site of application. Tacrolimus 0.03% is approved for use in ages 2 to 15 years. Known side effects to tacrolimus 0.03% include burning sensation, stinging, soreness, or pruritus at the site of application. These localized symptoms may occur during the first few days of use and subside as atopic dermatitis lesions improve. Subjects using tacrolimus should limit sun exposure and should not use ultraviolet light therapy, sun lamps, or tanning beds. Tacrolimus-treated skin should not be covered with bandages, dressings, or wraps. Contact of tacrolimus with eyes or mouth should be avoided. Unexpected side effects, such as allergic reactions, may occur and are unpredictable. This reaction may be mild, such as a skin rash, or you may have more severe symptoms like swelling of the throat, low blood pressure, and shortness of breath. If any of these unexpected side effects occur, subjects will be advised to stop use of their intervention immediately. Subjects will be informed about any additional potential risks if they are discovered. Furthermore, while we make every effort to keep all data and study information private, this cannot be guaranteed. All data will be de-identified and stored in a locked file in a locked office. All appropriate procedures will be taken to maintain subject privacy and data collected during this study.

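### Section 7's non-compliance criterion can be read to let the investigator withdraw and replace a child who stops the ointment, which would cost that child's 12-week itch and pain scores

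*Combined protocol and SAP*

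**What the plan says.** All references are to the combined protocol and SAP.

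- **Section 7 (Subject Withdrawals):** "Criteria for investigator-initiated subject withdrawal include: inability to make study visits, subject lost to follow-up, non-compliance to study procedures, or death". It adds: "Subjects that withdraw from the study will be replaced with another subject".
- **Section 5.6 (Subject Compliance):** "Subject compliance will be assessed using tube weight of the assigned topical treatment". The stated purpose of weighing at 6 and 12 weeks is to check that the ointment is being used. No weight limit is given.
- **Section 5.1 (Study Procedures):** "The topical treatments will be applied to all affected areas twice daily for at least 12 weeks on this study". Children under 5 "years will not complete any self-report measures on the iPad".
- **Section 10.1 (Potential Risks):** "Known side effects to crisaborole include pain at the site of application". "Known side effects to tacrolimus 0.03% include burning sensation, stinging, soreness, or pruritus at the site of application". These local symptoms are described as possible in the first days of use and as subsiding when lesions improve. For unexpected reactions such as allergy: "If any of these unexpected side effects occur, subjects will be advised to stop use of their intervention immediately".
- **Section 1.4 (Objectives):** the primary outcomes are the changes in PROMIS Itch and PROMIS Pain Interference after 12 weeks.
- **Section 11.1:** a child who completes at least the 6-week assessment counts as evaluable.
- **Section 11.2:** names ANCOVA, t-tests and longitudinal analyses. It defines no analysis set and no handling of missing 12-week scores.

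**The concern.** The symptoms most likely to make a child give up the ointment are pain and itch where it is applied, and the two primary outcomes are itch and pain interference. A removal rule that can be triggered by giving up the ointment may therefore select on something close to the outcome, after randomisation. The study is open-label (section 5.5), so the staff who apply the rule know the arm.

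If such children are removed and replaced, the 12-week comparison describes children who tolerated their ointment, not all children assigned to it. Withdrawal reasons are recorded (section 7) and adverse reactions are reviewed by arm (section 9.3), so the loss would be visible. The missing 12-week scores could not be recovered afterwards.

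**Working it through.** **1. Does the criterion reach a child who stops the ointment?** Section 7 does not say what non-compliance means. Section 5.6 is the only place that says how compliance is judged, and it uses ointment use. Section 5.1 places twice-daily application among the study procedures. Read together, these bring a child who stops or cuts down within the criterion. There is no exception for poor tolerability. The only rule that keeps a child on study (section 8) concerns flares and assumes that the assigned ointment continues.

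**2. What is lost, by time of removal?** Patient-reported outcomes are scheduled only at Baseline, 6 Weeks and 12 Weeks (section 13).

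| Non-use comes to light | How | Scores left if the child is withdrawn then |
|---|---|---|
| Week 3 | Phone call; no tube is weighed | Baseline only; not evaluable |
| Week 6 | Weighing, at the assessment visit | Baseline and 6 weeks; evaluable under 11.1, but no 12-week score |
| Week 9 | Phone call | As for Week 6 |
| Week 12 | Weighing, at the assessment visit | The 12-week score is due at the same visit, so it need not be lost |

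**3. How large could the shift be?** The plan gives no rate of stopping. Its nearest figure is the general allowance for withdrawal or dropout: 40 × 1.2 = 48 pairs, which reproduces the stated accrual. That allowance is not split by cause or by arm.

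Inputs from section 11.1: 20 children per arm, SD 10.0, effect 5.0 points.

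Assumptions:
- Ages are spread evenly over 2 to 15. Ages 5 to 15 are 11 of 14 single years, so 20 × 11/14 = 15.7, about 16 children per arm with itch and pain scores. The range shown is 12 to 20.
- One arm has s = 1 or 2 more removals than the other.
- Children who stop change by 0; the others improve by 5.0.
- SD 10 applies to the change score.

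With everyone kept, the arm with the extra stoppers has a mean improvement of 5.0 × (n − s)/n. After removal and replacement it is 5.0. The shift is 5.0 × s/n, and the standard error of the arm difference is 10 × √(2/n).

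| n per arm | Shift, s = 1 | Shift, s = 2 | SE | Shift/SE |
|---|---|---|---|---|
| 12 | 0.42 | 0.83 | 4.08 | 0.10, 0.20 |
| 16 | 0.31 | 0.63 | 3.54 | 0.09, 0.18 |
| 20 | 0.25 | 0.50 | 3.16 | 0.08, 0.16 |

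Against the plan's 5-point change, that is 0.25/5 = 5% to 0.83/5 = 17%.

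**4. A harsher set of assumptions.** Let an extra 10% to 15% of one arm stop (10% v 0%, 20% v 10%, or 20% v 5%), and let stoppers change anywhere from 0 to 5 points for the worse. The shift runs from 0.10 × 5 = 0.5 to 0.15 × 10 = 1.5 points. With 16 per arm that is 0.5/3.54 = 0.14 to 1.5/3.54 = 0.42 SE.

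**5. Equal stopping.** The arm difference does not move. Each arm's improvement from baseline is still overstated by 5.0/n per child removed, or 0.31 points with 16 per arm.

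**The case against.** The strongest reply is that the link between sections 7 and 5.6 is an inference. Section 7 does not mention tube weight and section 5.6 does not mention withdrawal. Section 8 puts continuing the study procedures and continuing the ointment in separate sentences, as if they were different things. Section 5.8 pays for completing the procedures and prorates by assessments completed. On that usage, the criterion concerns missed assessments only. This stands as a fair alternative reading. It makes the wording ambiguous, but it does not settle the matter, because section 5.1 still lists application among the procedures.

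Second, a tolerability stop has its own record. The AE Source Doc (section 5.3) has entries for interrupting or stopping the drug, separate from the Withdrawal Form. That shows stopping was foreseen, and for a child told to stop after an unexpected reaction the natural reading is that the child stays. It does not require later assessments, and it does not exempt anyone from the criterion.

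Third, the local symptoms may fade within days, and Pain Interference measures the effect of pain on daily activities, not pain at the application site. So few children may stop, and those who do need not have ointment-related pain at Week 12. This also stands, and it is one reason to expect a small effect.

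A reader might infer that any child who stops the ointment is removed and drops out of the analysis. The documents do not support that. The decision is the investigator's, there is no tube-weight threshold, and a child withdrawn after the 6-week assessment remains evaluable and may enter the longitudinal analyses with the 6-week score. Nor does section 7 say that a withdrawn child's collected data are discarded; replacement may be only an accrual rule.

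**Conclusion.** The point holds as a permitted and ambiguous removal, not an automatic one. If the criterion is applied to a child who has stopped the ointment, from the Week 3 call on and before Week 12, that child has no 12-week primary score. No provision requires follow-up after stopping.

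The resulting bias is probably small: 0.08 to 0.20 SE on the main assumptions, and up to 0.42 SE if stoppers worsen and 15% more of one arm stop. The number of stops, their outcomes and the age mix are all assumed. The point affects itch and pain only in children aged 5 or older.

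A reader might also infer that the rule favours crisaborole, since the trial expects it to be superior. The documents do not support a direction. The shift favours whichever arm has more removals, both ointments have known local side effects, and no stopping rates are given. This is a low-priority change, worth making because it is cheap and the lost scores cannot be recovered.

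**What to change.** **Section 7.** Limit the non-compliance criterion to missed assessments, and add: *A subject who stops or reduces the ointment for any reason, including advice under section 10.1, stays on study, completes the 6- and 12-week assessments and is not replaced for this reason.* The rule in section 8 on newly prescribed systemic therapy is not affected.

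**Section 5.6.** Keep tube weight as a description of use.

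**Section 11.2.** State that all randomised children aged 5 or older are analysed in their assigned arm for itch and pain, that any analysis limited to users is supportive, and that stops are reported by arm and reason. Families may still withdraw. Children enrolled afterwards then add to the sample and do not take the withdrawn child's place in the analysis.

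**Cost.** One short amendment. It needs no extra patients or visits: the 6- and 12-week visits are already scheduled and may be held by telemedicine, and fewer replacements would be needed.
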